Adverse events (AE) and serious adverse events (SAEs) are defined by the ICH for Clinical Safety Data Management (ICH-E2A), the Food and Drug administration as described in the section 9. Incidence of AE/SAEs will be summarized for each treatment group by body system and MedDRA term. The number and percentage of subjects with each body system and MedDRA term will be presented for each group. Pearson χ^2 test and/or Fisher Exact test were used to compare the frequency difference of AE and SAE between the treatment groups in System of Body (SOC) and Preferred Terms (PT) levels. Tables to summarize the incidence rates will be created for each of the following groups: Total AE and SAE, AE and SAE by relationship to study intervention, AE and SAE leading to premature discontinuation, AE and SAE presented in descending order of frequency by MedDRA term (no body systems shown). AE and SAE that led to premature discontinuation from the study will be listed. These listings will contain details about the SAEs such as outcome and relationship to study treatments. Other supportive data, such as the subject's age, will be given. All AE and SAE will be coded with MedDRA (updated version) and listed by subject.

Other analyses

Baseline characteristics

The patient demographics and pre-treatment baseline characteristics will be summarized for each treatment group and for all patients. The patient demographics such as age, race, gender, ethnicity etc. and baseline test results such as D-dimer, IL-6, LDH, ferritin, total WBC, absolute neutrophil count (ANC), absolute lymphocyte count (ALC), and testosterone will be analyzed. For continuous variables, the sample size, mean, median, SD, minimum, and maximum values will be calculated and tested either by Student t or Wilcoxon test depending on data distributions using SAS PROC TTEST and SAS PROC NPAR1WAY, respectively. For categorical variables, the number and percentage of patients by the intervention group will be tabulated and tested based on Pearson χ^2 test using SAS PROC FREQ.

Disposition status

Subject disposition will be summarized for the ITT population. The number and percentage of patients who completed or discontinued prematurely from the study by the treatment group will be tabulated and tested using Pearson χ^2 test. The number and percentage of patients who discontinued for each reason will be presented for each intervention group. The number and percentage of patients who completed or discontinued prematurely in each intervention group will also be displayed graphically.

Adherence

Patients who change the treatment groups after randomization or have protocol violations will be identified as non-adherence to the treatment. The number and percentage of non-adherence patients will be summarized by the treatment group and tested using Pearson χ^2 test.

Site Effect

Site effect will be evaluated for four participating sites. Balances of the treatment of assignment and the primary and secondary outcomes will be assessed among the four sites. If there is significant associations between the site and treatment assignment and a study outcome at significance level of 0.05 without multiplicity adjustment, the site effect will be adjusted in the corresponding the primary or any secondary outcome along with the other prognostic factors described in the primary and secondary analyses.

Table 3: Summary of Data Analysis Plan

Endpoint Analyses	Statistical Methods	SAS Procedures
Primary Endpoint A composite endpoint of mortality, hospital stay rate, and ECMO or mechanical intubation at 15 days after randomization	Pearson Chi-square tests or Fisher exact tests Logistic regression adjusted for Age, Hypertension, and COPD	1. PROC FREQ PROC LOGISTC
Secondary Endpoints 1. A composite endpoint of mortality, hospital stay rate, and ECMO or mechanical intubation at 30 days after randomization 2. Time to the clinical improvement 3. Inpatient Mortality 4. Length of Hospital Stay 5. Duration of Intubation for Mechanical Ventilation 6. Time to Normal Temperature 7. Maximum Severity of COVID-19 Illness	1. Pearson Chi-square tests or Fisher exact tests Logistic regression adjusted for Age, Hypertension, and COPD 2. Log-rank test, Kaplan-Meier curves Cox regression adjusted for Age, Hypertension, and COPD 3. Pearson Chi-square tests or Fisher exact tests Logistic regression adjusted for Age, Hypertension, and COPD 4. Wilcoxon test; quantile regression 5. Wilcoxon test; Quantile regression 6. Log-rank test, Kaplan-Meier curves Cox regression adjusted for Age, Hypertension, and COPD 7. Pearson Chi-square test; Cochran-Armitage trend test Proportional odds logistic regression	1. PROC FREQ PROC LOGISTC 2. PROC LIFETEST PROC PHREG 3. PROC FREQ PROC GENMOD 4. PROC NPAR1WAY PROC QUANTREG 6. PROC LIFETEST PROC PHREG 7. PROC FREQ PROC LOGISTC
Exploratory Analyses Clinical Prognostic Factors Laboratory Prognostic Factors Viral Load Cytokines Levels and TMPRSS2 Expression Germline genomic factors	1. Time to event data Log-rank tests, Kaplan-Meier curves and Cox regressions 2. Categorical data Pearson Chi-square tests and Logistic regression 3. Interval data Student t / Wilcoxon tests, linear or quantile regressions 4. Longitudinal data Mixed-effect model repeated measure	1. PROC LIFETEST PROC PHREG 2. PROC FREQ PROC LOGISTC 3. PROC TTEST PROC NPAR1WAY 4. PROC Mixed
AE/SAE Analyses 1. Incidence of AE/SAE 2. Frequency Difference of AE and SAE 3. AE /SAE by Relationship to the Treatment 4. AE/SAE leading to premature discontinuation	For All AE/SAE Incidence rate estimation and testing Pearson Chi-square tests or Fisher exact tests	PROC FREQ SAS Macros
Other Analyses 1. Demographics and Baseline Characteristics 2. Disposition Status 3. Study Protocol Adherence 4. Site Effect	1. Student t or Wilcoxon tests, Pearson Chi-square or Fisher Exact Tests 2. Pearson Chi-square Tests 3. Pearson Chi-square Tests 4. Pearson Chi-square Tests, Student t or Wilcoxon tests, log-rank test	1. PROC TTEST, PROC FREQ, PROC NPAR1WAY 2. PROC FREQ 3. PROC FREQ 4. PROC FREQ PROC LIFETEST PROC NPAR1WAY

Handling of Missing Data

Every effort will be made to minimize the occurrence of missing data, particularly for the primary and the secondary endpoints. In the event of a potential drop out, every effort will be made to capture missed data from the patient record and VA databases. For patients who drop out during the study the missing values for the primary endpoint analysis will be considered as failures. However multiple imputation (MI) method may be used for certain secondary endpoint analyses. Multiple imputations will be performed using SAS PROC MI under missing at random assumption. If the assumption does not hold, then imputations will be performed. Sensitivity analysis will be performed to compare the results from the various imputation scenarios.

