The COVID-19 pandemic is affecting a wide swath of the US population. Mortality from COVID-19 is higher in older, male patients. Given the demographics of the Veteran population, there is a critical need to develop therapies that can reduce the severity, mortality and duration of hospitalization for our Veteran population.

Selection and Description of Study Drug

Degarelix is an FDA-approved drug for prostate cancer. Of all the FDA-approved agents that inhibit AR signaling, degarelix exhibits the most rapid and robust effects. One loading dose of 240 mg subcutaneously (SQ) serves as a 30-day depot. As a luteinizing hormone releasing hormone (LHRH) antagonist, degarelix acts at the level the pituitary to rapidly reduce LH secretion, thereby decreasing testosterone production within the testes. A rapid reduction in circulating total testosterone to castrate levels is achieved in the majority of patients within 24 hours and virtually all patients in 2-3 days (see attached degarelix package insert). The testosterone level recovers after the 30-day depot is cleared. Degarelix was selected among other GnRH analogs due to its rapid effect on circulating testosterone, safety profile, and availability. For example, LHRH agonists (e.g. leuprolide) achieve castrate levels of testosterone over 2-3 weeks; the potent androgen receptor antagonists (e.g. enzalutamide and apalutamide) achieve steady-state in the serum over approximately 4 weeks. Clearly, these time frames for LHRH agonists and AR antagonists are not suited to testing in acutely ill patients with COVID-19.

Importantly, although LHRH analogs, including LHRH agonists and antagonists are well-tolerated in patients with advanced prostate cancer who represent an older population (median age ~66-68), there may be increased risk of cardiovascular complications. Risk of cardiovascular complication is associated with duration of exposure. For example, in a randomized controlled trial involving degarelix for patients with pre-existing cardiovascular disease with a median age of 72, ischemic cardiovascular events occurred in 3.4% of patients over 12 months of continuous therapy (DOI:

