All patients should commence assigned treatment as soon as possible and no later than 48 hours (2 calendar days) after randomization.

Stratification Factors

Patients will be stratified according to 3 factors:

- Age: <65 vs. ≥65
- History of hypertension prior to hospitalization: yes vs. no

- Influenza severity scale: 3 vs 4/5

Study site is not a stratification factor because the participating sites will be in close communication to minimize variability in providing BSC. Other potential factors that can influence clinical outcome include COPD, asthma, and cardiovascular disease will be assessed for their relationship to clinical outcome in exploratory analyses.

Blinding

This is a randomized, double-blind study. Patient treatment assignments will remain blinded. The study biostatisticians and clinical research pharmacist may access treatment assignment information as necessary.

The investigational drug blind will be maintained using the IWRS. The drug and placebo injections will be dispensed by the research pharmacy and packaged to be made indiscernible from one another. To maintain the blind, the IWRS will ensure the investigator or designee is unaware of the treatment arm assigned to the subject. Prior to dispensing the study medications, the research pharmacist will verify the appropriate treatment arm assignment using the IWRS cross-referencing the patient's randomization number. The study drug will be delivered to an unblinded administrator of the study drug who is not part of the study team and who will not disclose information regarding study drug administration to any member of the study team, the patient or anyone else.

Unblinding Procedure

The CSPCRPCC will not provide Emergency Code Envelopes to the Research Pharmacy for HITCH. Emergency unblinding will be managed through the 24-hour emergency call service [contact]). This number is also listed on the patient ID cards given to each patient participating in HITCH. The system managed by the CSPCRPCC will electronically capture up-to-date study drug assignment information gathered from the HITCH IWRS.

Authorization to Break the Blind

Under unusual circumstances, chiefly related to patient safety and emergency medical necessity, unblinding may be necessary if knowledge of the study treatment assignment will influence the medical treatment of the patient. This is usually done after consultation with the Study Chair.

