- *Possibly Related*: An event that follows a reasonable temporal sequence from administration of the study intervention follows a known or expected response pattern to the suspected intervention, but that could readily have been produced by a number of other factors.
- *Not Related*: The event is clearly not related to the investigational agent/procedure. - i.e. another cause of the event is most plausible; and/or a clinically plausible temporal sequence is inconsistent with the onset of the event and the study intervention and/or a causal relationship is considered biologically implausible.

Unanticipated Adverse Event:

An AE that is new or greater than previously known, in terms of nature, severity, or frequency of occurrence, or any other unanticipated serious problem associated with the investigation that relates to the rights, safety, or welfare of subjects, as documented in the protocol or other materials approved by the IRB of record or the characteristics of the study population. Such materials may include but are not limited to: the informed consent form, safety plan, clinical investigator's brochure (or CSPCRCC's Drug Information Report), and product labeling (see VHA Handbook 1058.01). The Sponsor (Cooperative Studies Program) will concur or disagree with the site investigator's assessment as to whether an adverse event is anticipated or unanticipated (sometimes referred to as expected/unexpected, respectively).

Expedited Reporting of Serious Adverse Events

All SAEs will be reported by submission of the event into the HITCH reporting system within 3 calendar days of the Study Site Personnel becoming aware of the event. The reporting system will immediately inform the Study Biostatisticians, Clinical Research Pharmacists and Study Chairs. All SAEs found to be attributable or related to the study intervention will be documented as "possibly related" or "related" within the SAE Form.

Expedited Reporting of Adverse Events of Special Interest

Cardiac arrhythmias and thromboembolic events will be considered AEs of special interest. Any cardiac arrhythmia or thromboembolic event of grade 3-5 according to Common Terminology Criteria for Adverse Events version 5.0 (CTCAE v5.0; see Appendix C) will be reported in a manner similar to SAEs, whereby the event will be reported to the HITCH reporting system within 3 calendar days of the Study Site Personnel becoming aware of the event.

Reporting of Related and Unexpected Serious Adverse Events

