9. SAFETY MONITORING

Data and Safety Monitoring Plan

The VA Clinical Sciences Research and Development (CSR&D) centralized Data Monitoring Committee (DMC) will monitor this study. The CSR&D DMC provides an ongoing independent evaluation of the progress of studies, including patient accrual and retention, adverse events monitoring, and analysis plan. This is a service that is provided by CSR&D to ensure independent oversight of the safety and integrity of this project. No other DMC or Data and Safety Monitoring Board (DSMB) review is needed.

The DMC office is located within the Cooperative Studies Program Coordinating Center (CSPCC) at the Edward Hines, Jr. VA Hospital in Hines, IL. The DMC Office at Hines then communicates directly with the PI to provide DMC related information.

After the DMC has recommended approval for this trial to begin and the first patient has been randomized, a progress report will be due in approximately one month and then monthly thereafter. The PI typically will not need to call in for the DMC review after the

initial review. The DMC makes recommendations to the director of CSR&D for endorsement. The recommendations range from approval (unconditionally or with conditions to be addressed) to probation to termination.

Following each DMC meeting, the PI will receive meeting minutes containing any action items for which a response will be requested typically within 30 days. Then the process starts all over again for the next reporting period. In addition to the quarterly progress reports, all Serious Adverse Events are to be reported to the DMC.

Additional Safety Monitoring for AEs of Special Interest

Whereas the DMC serves as the entity with primary oversight responsibility for the study, additional real-time monitoring will be conducted to capture AEs of special interest, including cardiac arrhythmias and thromboembolic events that may result from degarelix. In particular, cardiac arrhythmias and thromboembolic complications of grades 3-5 according to CTCAE v5.0 (see Appendix C) will be closely monitored through not only ongoing, daily review of AE and SAE reports, but also through regular, planned teleconference calls to include:

- The study chair ([name]), co-chair ([name]), and the lead site coordinator ([name]),
- One or more investigators from each site and/or one or more site coordinators.

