50%	Degarelix + BSC	64	72	84
	Placebo + BSC	32	36	42
	Total	96	108	126

Duration of Study and Number of Participating Sites

To estimate the expected study duration and resources, we assume that the recruitment rate will be half of what we anticipate. Under this assumption, various scenarios were examined in order to identify an optimal combination between the number of sites, the study duration (which includes recruitment period and follow-up period) and the estimated budget. The study will include four VA medical centers and each center will randomize 17 patients per month on average; however, estimated recruitment rate will vary depending on the patient volume of each participating center as the disease evolves. Based on these assumptions, the recruitment period was found to be approximately three

months. This will be followed by approximately one month of follow up for the last patients randomized into the study followed by one month of data analysis. Thus, the study duration including start-up will be approximately five months.

Interim Analysis and Criteria for Study Termination

A mid-term interim analysis of the primary endpoint will be performed at half of the patients or 99 randomized patients complete or are terminated the study. If the mid-term analysis of the primary endpoint indicates that the null hypothesis can be rejected with a boundary value of 2.77 (standardized $Z > 2.77$ or < -2.77) at an α -level of 0.006 or accepted with a boundary value of 0.44 ($-0.44 \leq \text{standardized } Z \leq 0.44$) based on O'Brien and Fleming criteria, the study will be recommended for trial termination for efficacy and futility reasons (shown in the Figure 1). Enrollment will be paused if the interim analysis results indicate crossing of the threshold for futility or efficacy until the final DMC recommendation is rendered.

Meanwhile, the drug toxicity will be closely monitored and analyzed. As described in previous sections, arrhythmia and thromboembolic complications are adverse events of special interest that will be monitored closely and graded according to on CTCAE 5.0. Once the toxicity markers reach a threshold of 25% (Ray and Rai 2011), a statistical analysis of the toxicity will be performed. If the experimental (degarelix) group has a significant higher toxicity compared to the placebo group at an α -level of 0.01, then results will be reported to the DMC for a recommendation for trial termination.

[figure not shown]

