### 3.8.2. Drug Toxicity Analysis

The drug toxicity will be closely monitored and analyzed. Cardiac arrhythmia and thromboembolic complications are adverse events of special interest (grade 3 and above) that will be monitored closely and graded according to on CTCAE 5.0. Once the toxicity markers reach a threshold of 25%, a statistical analysis of the toxicity will be performed. The treatment difference will be analyzed initially with a Pearson  $\chi^2$  test using SAS PROC FREQ (Table 3.8.2.1) and logistic regression will also be performed using SAS PROC LOGISTIC by taking account of prognostic factors described in the primary endpoint analysis (Table 3.8.2.2). If the experimental (degarelix) group has a significant higher toxicity compared to the placebo group at an  $\alpha$ -level of 0.01, then results will be reported to the DMC for a recommendation for trial termination.

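### A significantly worse toxicity result on degarelix leads only to a report to the DMC, with no enrolment pause while it decides, although an efficacy or futility crossing does pause enrolment

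*Protocol*

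**What the plan says.** Protocol section 10 (Interim Analysis and Criteria for Study Termination) sets out two stopping rules in adjacent paragraphs.

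- **Primary endpoint.** At the mid-term interim, a crossed boundary leads to a recommendation to terminate, and meanwhile: "Enrollment will be paused if the interim analysis results indicate crossing of the threshold for futility or efficacy". The pause lasts until the DMC's final recommendation. SAP 3.9 repeats the boundaries but not the pause.
- **Toxicity.** Once toxicity reaches 25%, the arms are compared. If degarelix is significantly worse at alpha 0.01, "then results will be reported to the DMC for a recommendation for trial termination". SAP 3.8.2 repeats this and specifies "adverse events of special interest (grade 3 and above". Neither text gives a reporting time or a pause.

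Other sections add safeguards:

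- Section 8, on SAE reports: "The reporting system will immediately inform the Study Biostatisticians, Clinical Research Pharmacists and Study Chairs". Section 4, on blinding: "The study biostatisticians and clinical research pharmacist may access treatment assignment information as necessary".
- Section 9 sends all SAEs to the DMC. On routine reporting it says that "a progress report will be due in approximately one month and then monthly thereafter". For these two toxicities it adds daily review of AE and SAE reports, weekly calls and 72-hour site reports.
- Section 8 foresees that the DMC may decide to pause. Section 9 sends DMC recommendations to the CSR&D director for endorsement.
- Section 1 provides for daily monitoring and correction of electrolytes and blood counts. Section 12 lets the IRB, OHRP or FDA stop the trial.

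**The concern.** The sponsor accepts that recruitment should wait while the DMC considers a crossed boundary, but writes this down only for benefit and futility. Waiting matters at least as much for harm, because the exposure cannot be reversed: "One loading dose of 240 mg subcutaneously (SQ) serves as a 30-day depot". There is no second dose to withhold. Monitoring can limit the consequences for a man already injected, but only a hold prevents a further injection.

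There is also a short queue of randomised but undosed men, since section 4 says: "All patients should commence assigned treatment as soon as possible and no later than 48 hours (2 calendar days) after randomization". The synopsis gives 24 hours. On a literal reading of the plan, men could still be randomised and injected while the DMC reviews a harm criterion that the trial has already met.

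**Working it through.** **1. The rules side by side**

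| Trigger | Source | Stated action | Enrolment | Undelivered doses |
|---|---|---|---|---|
| Efficacy or futility bound | Protocol 10 | Recommend termination | Paused | Not mentioned |
| Efficacy or futility bound | SAP 3.9 | Recommend termination | Not mentioned | Not mentioned |
| Toxicity at 0.01, degarelix worse | Protocol 10 | Report to DMC | Not mentioned | Not mentioned |
| Toxicity at 0.01, degarelix worse | SAP 3.8.2 | Report to DMC | Not mentioned | Not mentioned |

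The contrast is therefore about enrolment. No rule mentions undelivered doses. The safeguards listed above detect or decide; none sets a hold between the significant result and the decision.

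**2. The plan's accrual figure.** Section 10 gives four centres at 17 per month: 4 × 17 = 68 per month. 198 / 68 = 2.9 months, which agrees with the stated three months.

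**3. Exposure during review** (2:1 allocation, 30-day month)
- Per week: 68 × 7/30 = 15.9 men; × 2/3 = 10.6 on degarelix.
- At half that accrual: 7.9 men, 5.3 on degarelix.
- Review time is assumed: 3 days gives 6.8 men (4.5 on degarelix); 14 days gives 31.7 (21.2).

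**4. Randomised but undosed at any moment.** With the full 24-hour window, 68/30 = 2.3 men, 1.5 on degarelix. With the full 48-hour window, 4.5 men, 3.0 on degarelix.

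**5. Men still to enrol when the rule fires** on data from the first N: 198 − N − lag × 68/30, with the event lag assumed.

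| N | Lag 0 days | Lag 15 days | Lag 30 days |
|---|---|---|---|
| 66 | 132 | 98 | 64 |
| 99 | 99 | 65 | 31 |
| 150 | 48 | 14 | 0 |

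Zero lag is an upper bound. At a 60-day lag, the length of the protocol's AE collection period, no men remain even for N = 66.

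**6. Imbalance needed to fire.** The documents do not say whether the 25% is pooled or refers to the degarelix arm. At N = 99 (66 v 33), borderline patterns are:
- Pooled reading: 22/66 v 3/33 (Pearson p = 0.009, Fisher p = 0.013).
- Degarelix-arm reading: 17/66 v 1/33 (Pearson p = 0.006, Fisher p = 0.005).

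**7. Chance of firing at one look, N = 99.** Exact binomial calculation, with the Pearson test and the 25% gate; true rates are assumed.

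| True rates, degarelix v placebo | Pooled reading | Degarelix-arm reading |
|---|---|---|
| 20% v 10% | 0.3% | 3.5% |
| 30% v 15% | 9.5% | 14.7% |
| 25% v 25% | 0.2% | 0.4% |
| 30% v 30% | 0.4% | 0.4% |

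Repeated looks raise these figures, and the look schedule is not stated. With equal true rates of 25–30%, simulation gives a false trigger over the whole trial of about 1.0–1.7% with weekly looks and 0.5–0.9% with monthly looks.

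**The case against.** **Surveillance is close.** Daily review, weekly calls and 72-hour reports target exactly these events. The DMC receives every SAE, decides when to unblind itself and can pause. An imbalance like those above would build up in front of it before the formal rule fires. This stands, and it shrinks the gap to a short interval.

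**The pause used as a benchmark may stop nobody.** If completing the study means Day 60, the 99th man, randomised at about day 44 (99/68 × 30), completes at about day 104. Enrolment would have ended by about day 87 (198/68 × 30). This is fair on that reading of completion. It does not dispose of the point, because the toxicity rule is not tied to that interim and can fire earlier.

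**Leaving the pause to an independent DMC is defensible.** The comparison is unscheduled and may be repeated, and an automatic pause off the interim schedule could tell sites that harm was seen. The risk to the blind is real, and a neutral notice reduces it without removing it.

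**Stronger readings that the documents do not support**
- *That the plan orders dosing to continue after a harm signal.* It is silent; continuing is only the default.
- *That the efficacy or futility pause already holds doses.* It covers enrolment only.
- *That withholding the next dose is the only protection.* Dosed inpatients have daily electrolyte and blood count monitoring, with correction.
- *That a month's intake, 68 men, would be exposed.* This assumes that the DMC waits for its next monthly report. Section 10 ties the report to the toxicity result, which reads as event-driven.

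**Conclusion.** The gap is real but narrow. Both documents answer a significant harm result only with a report, and neither pauses enrolment until the decision, which itself has an endorsement step after the DMC's recommendation. At planned accrual the cost is about 16 men per week of review, about 11 on degarelix.

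This rests on an assumed DMC turnaround and on the rule firing at all, which needs a large imbalance: at one look at N = 99, even a true doubling of toxicity (20% v 10% or 30% v 15%) fires it in only about 0.3% to 15% of trials. An early or mid-trial trigger could spare tens of men if events are seen within about a month and review is slow. A late trigger spares few or none. No sample size, alpha or power figure is affected. The Operations Manual was not available and may already contain a hold. The change is worth making as a cheap improvement; the plan should not be read as lacking safety control.

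**What to change.** Leave the efficacy and futility sentence as it is. Add to protocol section 10 and SAP 3.8.2:

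> If the toxicity comparison meets the 0.01 criterion with degarelix worse, the result will be sent to the DMC the same day, and enrollment and any study doses not yet given will be paused until the DMC recommendation has been rendered and acted on by the CSR&D director. A dose window missed because of the pause is not a protocol deviation, and undosed men are excluded from the toxicity comparison.

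The dose hold deliberately goes beyond the existing pause. The last clause is needed because the Safety population is all randomised patients, so held men would otherwise enter the toxicity denominator. They stay in ITT under the existing definition. Section 8 names the CSP Director as recipient of the DMC's safety advice and section 9 the CSR&D director, so confirm who acts. Send sites a neutral pause notice that does not give the cause. If the Operations Manual already has such a hold, cite it here instead.

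**Cost.** One added passage in each document, with no new threshold or committee. If triggered:
- about 16 men of accrual are delayed per week;
- up to about 3 degarelix men go undosed but stay in ITT, diluting the planned 25-point difference by about 0.6 points (3/132 × 25);
- sites may infer harm;
- the false-trigger chance is about 0.2–0.4% per look at equal true rates of 25–30%.
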